7 STUDY PROCEDURES/EVALUATIONS

7.1 Study Procedures/Evaluations

7.1.1 Oral Cancer Screening Examination

- (1) The oral cancer screening examination will be conducted between the baseline and final study visit.
- (2) The RC will facilitate scheduling of this visit with a participating, licensed Head and Neck Specialist.
- (3) The oral cancer screening examination may involve:
 - a. The palpation of the neck, mouth and base of tongue;
 - b. Possible indirect examination of the base of tongue by use of mirror or flexible fiber-optic laryngoscope at the discretion of the specialist; and
 - c. Soft tissue abnormalities, which will be recorded on study-specific case report forms (CRFs).
- (4) Any abnormal findings will be evaluated and treated per the standard of care at the expense of the participant/participant's insurance. This may include a referral to a Head and Neck Specialist in the patient's insurance network.

7.1.2 HPV Results Reporting

- (1) High-risk oral HPV test results from a patient's oral rinse sample will be reported to practitioners via the study's secure, password-protected web-based application within a week of the sample's receipt at the [name] HPV detection laboratory (located at the Polaris Innovation Center, [name], Columbus, OH 43240).
- (2) A 3-tiered approach will be implemented to inform patients of test results:
 - a. The dentist will be the first to provide the patient with their high-risk HPV test result via phone (Sections 6.2.1 and 6.2.2);
 - b. If necessary, a trained RC (one from each region) will speak with the patient to address their questions; and
 - c. After the RC has addressed questions, the patient may contact the SPI, [name] with additional questions (pilot study only).
- (3) The dentist will offer to send the patient a copy of their high-risk HPV results report (Appendix Q: HPV Results Template) along with a letter of interpretation (see Appendix R and S: Results Reporting Letter for Positive and Negative Results, respectively), so that he or she may take it to his or her physician for follow-up.

7.2 Laboratory Procedures/Evaluations

7.2.1 Oral Rinse Sample (10mL)

- (1) Standard operating procedures (SOPs) will be used for specimen processing, DNA purification and HPV detection; See MOP: Laboratory SOPs.
- (2) High-risk types of HPV include 16, 18, 31, 33, 35, 39, 45, 51, 52, 56, 58, 59, 68, and 73.
- (3) Samples found to be β -globin negative will be reported “inevaluable.”
- (4) Oral rinse samples may undergo evaluation for additional biomarkers, such as detection of HPV E6 protein.

7.2.2 Blood Serum Sample (10mL)

Samples will be evaluated for HPV 16, 18, 31 and 35. Sera will also be evaluated for the presence of antibodies to HPV viral proteins, specifically E6 and E7 antibodies, through a proprietary test.

7.2.3 Specimen Banking

- (1) Participants may be asked during the consent process if they agree to donate their oral rinse sample(s) and blood samples to be stored for future research.
- (2) If the participant agrees, his/her sample(s) will only be used by the principal investigator for research related to oral cancer risk and may include the evaluation of genes related to the risk of oral/oropharyngeal cancers.

7.3 Study Specific Biospecimens

See *MOP, Section 10: Specimen and Laboratory Management*, for detailed information regarding Oral Rinse and Blood Sample Collection, Labeling, Shipping and Handling Procedures.

7.3.1 Specimen Collection

7.3.1.1 Oral rinse

- (1) An oral rinse is only to be collected from individuals selected by the web application.
- (2) An oral rinse consists of a 30 second swish and gargle with ScopeTM mouthwash.
- (3) An oral rinse sample should be collected by a study-trained dentist, dental hygienist or dental assistant, as determined by the site or practitioner; the staff member collecting the rinse will be guided by an oral rinse collection tool and timer on the web application.
- (4) An oral rinse sample should be collected when the patient arrives in the dental exam room, prior to the patient’s dental exam or cleaning.

7.3.1.2 Blood

- (1) A blood sample is only to be collected from individuals enrolled in the follow-up (longitudinal) component of the study.
- (2) The blood sample may be collected at one of the following locations (determined by the RC and practitioner prior to study initiation):
 - a. Clinical laboratory
 - b. Community hospital
 - c. Mobile phlebotomy service (e.g., HEI)
 - d. Participating dental practice (with an on-site RN or phlebotomist)
 - e. Participating specialist's office
- (3) The blood sample should be collected in a single red-top (blood serum) tube by a clinical or laboratory professional trained in drawing blood, using a CC-provided, pre-labeled blood sample collection kit.
- (4) Participating blood-draw locations will be compensated for the time required to do the research, according to their usual collection for the procedures.

7.3.2 Specimen Preparation, Handling and Storage

7.3.2.1 Oral rinse

- (1) The sample must be stored at 4°C in the practice's designated biohazard refrigerator until shipping.
- (2) If necessary, the sample may be stored or transported in a cooler with ice packs for up to 4 hours until refrigeration is possible.

7.3.2.2 Blood

- (1) The blood sample must be left to coagulate at room temperature for 30 minutes.
- (2) After 30 minutes, the blood sample must be stored at 4°C until it is shipped.
- (3) If necessary, the sample may be stored or transported in a cooler with ice packs for up to 4 hours until refrigeration is possible.

7.3.3 Specimen Shipment and Tracking

7.3.3.1 Oral rinse

- (1) A sample must be shipped from the dental practice to the [name] HPV detection laboratory (located at the Polaris Innovation Center, [name], Columbus, OH 43240) within five business days of its collection.
- (2) Multiple samples may be shipped together in batches weekly or twice weekly.
- (3) Shipping instructions, supplies and prepaid air bills will be provided by the CC.

7.3.3.2 Blood

- (1) Blood samples must be shipped to the Ohio State University lab on the day they are drawn.
- (2) Shipping instructions, supplies and prepaid air bills will be provided by the CC.

7.4 **Electronic Questionnaires**

7.4.1 **Administration**

The following questionnaires (surveys) will be administered as described in Section 6.2 (dependent on the part(s) of the study the patient is participating in):

- (1) Electronic oral HPV risk factor survey (Appendix C)*
 - a. Purpose: To determine patient's oral HPV risk profile; based upon questionnaire responses, both high- and low-risk patients may be selected for oral rinse sample.
 - b. Completed by: Patient
 - c. Length: 10-20 questions
 - d. Duration: Lower completion time is 2 minutes, upper completion time is 6 minutes
- (2) Electronic oral cancer risk factor survey (Appendix J)*
 - a. Purpose: To administer a detailed risk factor survey to determine baseline and lifetime measures of factors known to be associated with risk of oral cancer. Many of these factors are also associated with oral HPV infection (e.g., sexual behavior, smoking).
 - b. Completed by: Patient
 - c. Length: 37-147 questions
 - d. Duration: Lower completion time is 5 minutes, upper completion time is 35 minutes
- (3) Provider survey (Appendix P)
 - a. Purpose: To assess feasibility and acceptability of study procedures among dental staff.
 - b. Completed by: Dentist, dental assistant, dental hygienist or other dental administrative staff
 - c. Length: 19 questions
 - d. Duration: Lower completion time is 3 minutes, upper completion time is 6 minutes

Surveys marked with an asterisk (*) in the list above are based on previously validated instruments used in National Health and Nutrition Examination Survey (NHANES) and previous [name] lab case-control and epidemiological studies.

The oral HPV risk factor survey questions are compiled from questions used in the NHANES 2009-2010 study cycle, which were administered to almost 5,000 NHANES study participants, and were used in the development of the model analyzing sociodemographic and behavioral risk factors associated with oral HPV infection.

The oral cancer risk factor survey was derived from several large-scale population-based surveys, as well as prior [name] research team study surveys. Questions in the detailed risk factor survey are derived from validated sources such as NHANES (demographic, sexual behavior), the Behavioral Risk Factor Surveillance System (demographic), the Lifetime Tobacco Use Questionnaire (tobacco, and modified for alcohol and marijuana), and [name] research team surveys (see D'Souza G, et al, NEJM 2007; tobacco, alcohol, marijuana, and sexual behavior). The cancer history section was derived from a questionnaire developed by the James Cancer Center for assessing cancer risk based on personal and familial cancer history. Modified versions of the follow-up detailed risk factor survey using a computer assisted self-interviewing (CASI) format on tablet computers have been administered to over 800 participants in the RTOG1016 study and over 700 participants in a 5-year case-control study currently being conducted by the [name] research team.

7.4.2 Technology

- (1) Study procedures and electronic questionnaires will be administered within a secure web-based application accessed via tablet computers.
- (2) A secure, password-protected wireless router is required in order for a practitioner to participate in this study; See MOP: *Site Initiation SOP*.
 - a. Practitioners without a wireless internet connection will be provided with a secure, study-sourced wireless router prior to study initiation.
- (3) One to two tablet computers will be provided to each participating practitioner, depending on their enrollment rate and patient volume; See MOP: *Site Initiation SOP*.

7.4.3 Training and Troubleshooting

- (1) RCs will be trained on how to operate the tablet computers and the web application via web seminar with the Ohio State University Clinical Data Manager. See MOP: *Web Application User Guide*.
- (2) Participating practitioners and their staff members will be trained on tablet computer and web application operation by their regional RC. See MOP: *Web Application User Guide*.

8 ASSESSMENT OF SAFETY

8.1 Specification of Safety Parameters

Safety monitoring for this study will focus on unanticipated problems involving risks to participants, including unanticipated problems that meet the definition of a serious adverse event (SAE).

8.1.1 *Unanticipated Problems*

The Office for Human Research Protections (OHRP) considers unanticipated problems involving risks to subjects or others to include, in general, any incident, experience, or outcome that meets **all** of the following criteria:

- (1) Unexpected in terms of nature, severity, or frequency given (a) the research procedures that are described in the protocol-related documents, such as the IRB-approved research protocol and informed consent document; and (b) the characteristics of the subject population being studied;
- (2) Related or possibly related to participation in the research (possibly related means there is a reasonable possibility that the incident, experience, or outcome may have been caused by the procedures involved in the research); and
- (3) Suggests that the research places subjects or others at a greater risk of harm (including physical, psychological, economic, or social harm) than was previously known or recognized.

8.1.2 *Serious Adverse Events*

An SAE is one that meets one or more of the following criteria:

- (1) Results in death
- (2) Is life-threatening (places the subject at immediate risk of death from the event as it occurred)
- (3) Results in inpatient hospitalization or prolongation of existing hospitalization
- (4) Results in a persistent or significant disability or incapacity
- (5) Results in a congenital anomaly or birth defect

An important medical event that may not result in death, be life threatening, or require hospitalization may be considered an SAE when, based upon appropriate medical judgment, the event may jeopardize the patient and may require medical or surgical intervention to prevent one of the outcomes listed in this definition.

8.2 Reporting Procedures

Incidents or events that meet the OHRP criteria for unanticipated problems require the creation and completion of an unanticipated problem report form. OHRP recommends that investigators include the following information when reporting an AE, or any other incident, experience, or outcome as an unanticipated problem to the IRB:

- (1) Appropriate identifying information for the research protocol, such as the title, investigator's name, and the IRB project number.
- (2) A detailed description of the AE, incident, experience, or outcome.
- (3) An explanation of the basis for determining that the AE, incident, experience, or outcome represents an unanticipated problem.
- (4) A description of any changes to the protocol or other corrective actions that have been taken or are proposed in response to the unanticipated problem.

To satisfy the requirement for prompt reporting, unanticipated problems will be reported using the following timeline:

- (1) Unanticipated problems that are SAEs will be reported to the IRB and to NIDCR within one week of the investigator becoming aware of the event.
- (2) Any other unanticipated problem will be reported to the IRB and to NIDCR within two weeks of the investigator becoming aware of the problem.
- (3) All unanticipated problems should be reported to appropriate institutional officials (as required by an institution's written reporting procedures), the supporting agency head (or designee), and OHRP within one month of the IRB's receipt of the report of the problem from the investigator.

All unanticipated problems will be reported to NIDCR's centralized reporting system via Rho Product Safety:

- (1) Product Safety Fax Line (US): [name]
- (2) Product Safety Fax Line (International): [contact]
- (3) Product Safety Email: [contact]

General questions about SAE reporting can be directed to the Rho Product Safety Help Line (available 8:00AM – 5:00PM Eastern Time):

- (1) US: [name]
- (2) International: [contact]

9 STUDY OVERSIGHT

In addition to the GPI's and Study Principal Investigator's (SPI) responsibility for oversight, study oversight will be under the direction of the PBRN Data and Safety Monitoring Board (DSMB) composed of members with expertise in dentistry, practice-based research, study design and statistics. The DSMB will meet at least annually to assess safety and efficacy data for the study. If safety concerns arise, more frequent meetings may be held. The DSMB will operate under the rules of an NIDCR-approved charter that will be approved at the organizational meeting of the DSMB. At this time, most data elements that the DSMB needs to assess will be clearly defined. The DSMB will provide recommendations to the NIDCR.

10 CLINICAL SITE MONITORING

Clinical site monitoring is conducted to ensure that the rights of human subjects are protected, that the study is implemented in accordance with the protocol and/or other operating procedures, and that the quality and integrity of study data and data collection methods are maintained. The network RAS will be responsible for clinical site monitoring for this study. RCs at each RAS will provide study training to practitioner sites and perform clinical site monitoring activities, to evaluate study processes and documentation based on NIDCR standards and principles of good clinical practice.

All details about clinical site monitoring will be documented in a Clinical Monitoring Plan (CMP) developed by Westat, under the direction of the National Dental PBRN, in collaboration with the NIDCR Office of Clinical Trials Operations and Management (OCTOM) and the NIDCR Program Official. The CMP will specify practitioner training activities, the type and frequency of monitoring, monitoring procedures, the level of clinical site monitoring activities (e.g., the percentage of patient data to be reviewed), and the distribution of monitoring reports. Some monitoring activities may be performed remotely, while others will take place at each practitioner site. The RCs will provide reports of the findings from monitoring and associated action items in accordance with the details described in the CMP. Documentation of monitoring activities and findings will be provided to the practitioner, GPI, SPI, OCTOM, and the NIDCR. The NIDCR reserves the right to conduct independent audits as necessary.

11 STATISTICAL CONSIDERATIONS

Statistical considerations, including sample size and power calculations, are further detailed in the Statistical Analysis Plan (SAP).

11.1 Study Hypotheses

This pilot study is designed to test the following hypotheses:

- (1) The proportion of the high-risk HPV infection among individuals selected for oral rinse collection will be similar to the proportion predicted by the risk factor model;
- (2) Baseline study procedures will be feasible and acceptable to dental practice staff and patients;
- (3) The distribution of demographic and behavioral risk factors in the study population will be similar to the US population; and
- (4) Participants will be compliant with follow-up study procedures, including the blood draw, oral cancer screening examination, second oral rinse specimen collection and detailed oral cancer risk factor survey (Appendix J); and
- (5) Arranging and conducting the procedures will be feasible for RC and dental practice staff.

The study will determine whether or not oral HPV detection can be used to identify individuals in a dental practice who are at high-risk for HPV-associated oral cancer and who should be targeted for referral and screening for oral cancer.

11.2 Sample Size Considerations

The sample size for this pilot study is based upon a dichotomous outcome in which participating patients are categorized as low-risk versus high-risk for oral high-risk HPV infection. Based upon our risk model derived from 5,500 individuals who are representative of the US population (NHANES), we expect 30% of the study population to be categorized as high-risk. A two-sided test of proportions with a type 1 error of 0.05 indicates that a pilot study with 1,000 individuals will have 90% power to detect a 5% or greater difference in the proportion of the study population that is categorized as high-risk. The ability to enroll a sample size of 1,000 will also provide assurance that a study with a large sample size is feasible in the National Dental PBRN.

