Although commercial tests for oral HPV detection are not validated, the [name] laboratory has developed and validated methods for reproducible detection of oral HPV infection and demonstrated the ability to detect type-specific persistence of infection over time⁶⁻¹⁰. These methods were recently used to examine the prevalence of oral HPV infection in the US population in collaboration with the US Centers for Disease Control and Prevention (CDC)¹¹. In this analysis, age, gender, number of sexual partners and current number of cigarettes smoked per day were associated with oral HPV infection. A very brief questionnaire designed to assess these factors can therefore identify the subset of the population most likely to have a prevalent, oral high-risk HPV infection.

A simple 30-second oral rinse and gargle can be used to detect oral HPV infection by any of the HPV types linked to development of cancer. Additionally, blood sera can be evaluated for the presence of antibodies to HPV viral proteins. A recent publication has indicated that the presence of these antibodies may identify individuals with oral HPV infection who are at risk for progression to invasive, HPV-positive oral cancer (Kreimer A. et al JCO 2014).

The US Preventive Services Task Force does not have a recommendation for or against routine screening for oral cancer (inclusive of oral cavity and oropharynx cancers)¹². The standard of care for detection of oral cancer remains opportunistic screening involving physical examination by an experienced clinical practitioner during a routine dental or medical visit. One objective of this pilot proposal is to evaluate feasibility and acceptability of study procedures necessary to accomplish the aims of a future larger study in the National Dental Practice-Based Research Network (PBRN). All of the procedures in this pilot will be identical to those performed as part of the cross-sectional component and one 6-month follow up (window: 5-9 months) of a future larger study. Individuals with oral high-risk HPV infection detected at baseline will also be referred to a head and neck specialist for a standard oral cancer screening examination with visual inspection and palpation. The head and neck specialist performing the examination may be an otolaryngologist or an oral and maxillofacial surgeon trained to perform indirect mirror and flexible fiber optic visualization and palpation of the base of tongue.

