5.2.3 Patient

A patient who meets any of the following criteria will be excluded from participation in this study:

- (1) A history of head and neck cancer, inclusive of cancers of the sinus, oral cavity, pharynx and larynx;
- (2) Received the HPV vaccine;
- (3) Inability to understand study procedures or provide consent in English or Spanish; and
- (4) Intention or expectation to relocate or to change dental provider within six months.

Depending on dental practice policies and institutional review board requirements, participating practices may add, as exclusion criterion (5), 'the absence of medical insurance.'

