11.3 Final Analysis Plan

To accomplish the primary objective, our outcomes of interest will be the number of individuals determined to be in the top three deciles of risk based on our model (i.e., those selected for oral sample collection based on risk) as well as the proportion of those individuals with an oral high-risk HPV infection. Based upon our model in NHANES, we would expect that 30% of the participating population would be selected for specimen collection and that the resulting population would have an oral high-risk prevalence of 8.43% (95%CI 6.68% to 10.14%). The number of individuals selected as high-risk will be informative with regard to the distribution of

risk factors in the study population, and the proportion positive will be informative with regard to the β -estimates for our risk model.

Shown in the table below are the upper and lower bounds of the 95% CI for the proportion positive for oral high-risk HPV infection, assuming a range of 10-50% of the study population is categorized as high-risk based on our model. A proportion of the study population with oral high-risk infection that falls within the confidence bounds in the table below, given the sample size, will indicate that the β -estimates in our NHANES model are reasonable estimates of risk to the study population.

Sample size	Proportion	95% Confidence Interval	
		Lower Bound	Upper Bound
100	8.43%	2.98%	13.88%
200	8.43%	4.58%	12.28%
300	8.43%	5.29%	11.57%
400	8.43%	5.71%	11.15%
500	8.43%	5.99%	10.87%

To accomplish secondary objectives (1) and (3) a brief Provider Survey (Appendix P) will be administered via tablet computer/web-application to providers at each participating practice to assess acceptability of each procedure and willingness to participate in a future larger study. Results will be reported as summary statistics.

Descriptive statistics for secondary objective (3) include the proportion of individuals with high-risk oral HPV infection who:

- (1) Enroll in the follow-up study;
- (2) Attend a 6-month follow-up;
- (3) Provide blood serum sample; and
- (4) Provide second oral rinse.

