To accomplish secondary objective (2) the distribution of the demographic and behavioral variables in the study population will be compared to the weighted distribution of the same factors in the US population per NHANES. In this analysis, the distribution of the populations into deciles of risk will be represented in an $n \times k$ table where n represents the two populations and k the deciles of risk. The distribution will be compared by chi square test with nine degrees of freedom. The distribution of each variable in the two populations will also be compared in univariate analysis. Successful completion of this pilot will therefore: (1) assess patient acceptability of the procedures; (2) provide training to study personnel and assess the feasibility of incorporating the study procedures into clinical practice; and (3) inform the point estimates and models used for sample size determination for a future larger study to ensure that the estimate of 60,000 screened individuals is appropriate.

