14.4 Exclusion of Women, Minorities, and Children (Special Populations)

All men and women between the ages of 30-69 years will be eligible to enroll in this study. Individuals under the age of 30 years are excluded from participation because data from the US population indicate this age group is at extremely low risk for high-risk oral HPV infection and oral cancer.

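### The 30% high-risk expectation and the NHANES comparison distributions are set on the US population, with no stated restriction to people the trial can enrol

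*Protocol*

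**What the plan says.** **The reference.** Section 11.2 bases its expectation on "our risk model derived from 5,500 individuals who are representative of the US population (NHANES), we expect 30% of the study population" to be classed as high-risk. Section 11.3 repeats it: "Based upon our model in NHANES, we would expect that 30% of the participating population would be selected for specimen collection". Hypothesis 3 in section 11.1 is that risk factors in the study population resemble those of the US population. For secondary objective 2, section 11.3 compares the study variables with the "weighted distribution of the same factors in the US population per NHANES". It does so through a two-population by ten-decile chi-square test on 9 degrees of freedom and through univariate comparisons of each variable. Section 3.2 lists age among those variables.

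**The study population.** Section 5.1.3 admits ages 30 to 69 only. Section 5.2.3 excludes people with a history of head and neck cancer and anyone who has "Received the HPV vaccine".

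**The link between the two.** Section 2.2 reports that "age, gender, number of sexual partners and current number of cigarettes smoked per day were associated with oral HPV infection". Section 14.4 justifies excluding under-30s because "data from the US population indicate this age group is at extremely low risk for high-risk oral HPV infection".

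**The test.** Section 11.2 specifies "A two-sided test of proportions with a type 1 error of 0.05" and claims that "1,000 individuals will have 90% power to detect a 5% or greater difference in the proportion of the study population" classed as high-risk.

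**The concern.** Age is one of the factors associated with infection in the analysis behind the risk questionnaire, and the protocol itself places under-30s low on the risk scale. If such people are in the reference that defines the deciles, removing them by eligibility raises the share of the remaining people above any fixed cut-point. The comparison with 30%, the decile test and the age comparison would then partly measure the eligibility criteria rather than how dental-practice patients differ from their peers.

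This matters because section 11.3 reads the number selected as information on the risk-factor distribution of the study population, and uses the pilot to check the figure of 60,000 screened individuals for the larger study. An eligibility effect could be mistaken for a feature of dental patients. The planned number of rinses also rests on the 30%.

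**Working it through.** **Inputs from the protocol:** N = 1,000; benchmark 30%; two-sided alpha 0.05; reference n = 5,500; detectable difference 5 points (all section 11.2); ten deciles, 9 df (section 11.3).

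**Assumed, because the protocol does not give them:** f, the ineligible share of the reference, and g, the fraction of those ineligible people who fall in the top three deciles. Reference and study samples are treated as simple random samples.

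**1. The plan's own figure.** Comparing two proportions, 30% in 5,500 and 25% in 1,000, gives power 0.901, which reproduces the stated 90%. The same test with 35% gives 0.877. A one-sample test against a fixed 30% gives 0.943 (at 25%) and 0.924 (at 35%).

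**2. Expected share in a perfectly representative eligible sample.**

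q = (0.30 - g·f)/(1 - f), which is 0.30/(1 - f) when g = 0.

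With g = 0, q reaches the protocol's own 5-point difference when f = 1 - 0.30/0.35 = 14.3%.

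**3. Chance of rejecting 30% (one-sample).** The standard error under 30% is √(0.30 × 0.70/1000) = 0.01449, so the upper rejection limit lies 1.96 × 0.01449 = 0.0284 above 30%. The rejection probability is Φ[(q - 0.30 - 0.0284)/√(q(1 - q)/1000)], plus a negligible lower tail. Example at f = 10%: (0.0333 - 0.0284)/0.01491 = 0.33, so the probability is 0.63.

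**4. Decile chi-square.** With f spread evenly over deciles 1-7, each low decile holds (0.70 - f)/[7(1 - f)] of the eligible sample and each top decile holds 0.10/(1 - f). This is set against 10% per decile, with 1,000 and 5,500 people, using the noncentral chi-square on 9 df. At f = 20% the cells are 8.93% and 12.5%.

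Results with g = 0:

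| f | Expected high-risk share | Rejects 30%, one-sample | Rejects 30%, two-sample vs 5,500 | Decile test rejects |
|---|---|---|---|---|
| 0 | 30.0% | 5% | 5% | 5% |
| 5% | 31.6% | 20% | 17% | 8% |
| 10% | 33.3% | 63% | 56% | 25% |
| 14.3% | 35.0% | 92% | 88% | 56% |
| 20% | 37.5% | 99.9% | 99.6% | 94% |

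**5. Relaxing g.** At f = 20%, g = 10% gives q = (0.30 - 0.02)/0.80 = 35.0%, rejected 92% of the time (one-sample); g = 20% gives (0.30 - 0.04)/0.80 = 32.5%, rejected 41%. At g = 30% the effect vanishes.

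**6. Univariate age comparison.** This needs no assumption about deciles. The study has no under-30s by design. If the reference had 5%, that is 275/5,500 against 0/1,000, the pooled proportion is 275/6,500 = 0.0423 and chi-square = 0.05²/[0.0423 × 0.9577 × (1/1000 + 1/5500)], about 52. At 1% (55/5,500) it is about 10, p about 0.0015.

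**7. Rinses.** The plan: 300 + 700/12, about 358 (the protocol gives about 359). At f = 20% and g = 0: 375 + 625/12, about 427.

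**The case against.** The strongest reply is that the protocol never says who the 5,500 are. A sample described as representative of the US population could be a weighted subset in the eligible age range, and sections 11.2 and 11.3 state the 30% as an expectation for the study or participating population. Section 11 also sends further detail to the SAP, where the choice of NHANES records might be specified. The first part stands: the size of the problem cannot be fixed from the document, and may be zero. The second does not remove the point, because the protocol itself names the comparator, the 30%, the test and the hypothesis, and as named they are not like-for-like with the study population.

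It is also fair that no formal decision depends on rejecting 30%, and that an age imbalance would be visible in the univariate output. That lowers the stakes but leaves the misattribution possible.

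Three stronger readings are tempting, and the document supports none of them:

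- **A representative sample is bound to be declared different.** Near-certain rejection needs f of about 20% with almost all excluded people in the lower deciles. At f = 5% rejection is 20% or less. Very low risk in section 14.4 describes a group's infection and cancer risk, not each member's model score, which may also reflect gender, partners and smoking.
- **The 8.43% prevalence benchmark is wrong too.** It is conditional on being in the top three deciles, so removing people below them leaves it unchanged. With g of 10-20%, f of 20-30% and an assumed prevalence of 3-5% among excluded people in those deciles, it becomes about 8.7% to 9.8%. The estimate would still fall in a 95% band built as in section 11.3 about 83-94% of the time.
- **The vaccine exclusion has its own measurable effect.** The protocol gives neither the vaccinated share nor the risk of vaccinated people. The effect of leaving out over-69s is equally unknown.

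**Conclusion.** The point holds in conditional form. As written, the 30% expectation, the decile reference and the univariate reference are those of the US population, while the trial samples a restricted part of it whose excluded young group the protocol calls very low risk. If the reference includes ineligible low-risk people, the comparison mixes eligibility with any difference due to dental practice. At f = 14.3% and g = 0 the shift equals the 5-point difference the study is sized to detect. The size depends on f and g, neither of which is given. It is small at f = 5%, large at f = 20% unless a fair fraction of those excluded score high, and nil if the reference is already restricted. If the reference contains under-30s at all, the age comparison differs by design. The figures ignore the NHANES survey design, which would generally lower the two-sample and decile rejection rates. The change is worth making before analysis.

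**What to change.** - In 11.2 and 11.3, compute the expected high-risk share and every NHANES comparison distribution, with survey weights, in NHANES participants who meet the trial's criteria: at least age 30-69, plus vaccination and head and neck cancer history where NHANES holds them. Use these values in place of 30% and 10% per decile. If the 5,500 are already that subset, say so; the figures then stand.
- In 11.1, reword hypothesis 3 as similarity to the eligible US population.
- Reconcile the NHANES count: 5,500 in 11.2 against just under 5,000 in 7.4.1. This barely affects power (0.901 against 0.897), but the reader needs to know which records form the reference.

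The cost is one re-tabulation of existing data and some wording. The web application's cut-points and trial conduct need not change.
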